## **8.B. Patient Survey for patient-reported outcomes**

All study-enrolled patients (n=2000) will be invited to complete a series of surveys that will be the source of the patient-reported primary outcomes (i.e., treatment side effects, experiences and satisfaction with hypertension care, self-management support, confidence in self-care). Appendix H Figure 1 describes the process for collecting survey data from patients. The EHR tool will identify patients at the visit when they are enrolled in the study and transmit their contact information to the HealthPartners Survey Research Center (SRC). The SRC will mail a letter to request their participation in a series of surveys, a paper questionnaire and a \$2 non-contingent incentive, a practice known to increase response rates and reduce the likelihood of non-response error. The SRC's professional phone interviewers will call patients who do not return the paper survey to attempt to complete a survey via phone within 2 weeks of enrollment. At the end of the survey, respondents will be asked what mode they prefer for follow-up surveys 6, 12 and 24 months later. First contact for follow-up surveys will be made via the respondent's preferred mode. Non-respondents to the enrollment survey will not receive further surveys. All four surveys (enrollment, 6, 12, and 24 months) will include the patient reported outcome measures. The secondary analyses (H1.2) will make use of data collected from the enrollment and 6m surveys while other outcome analyses will make use of data collected at all four time points. Patients who complete enrollment, 6, 12, and 24 month surveys will be mailed a \$10 gift card. Patients who are on the HealthPartners Institute Exclusion List will not receive a survey.

## **9. Evaluation Reporting**

Clinic managers and primary care physician chiefs will be provided with a monthly summary of measures pertaining to their blood pressure care and the study interventions. The reports will include measures found in Tables 2 and 3, and will be linked to clinics' blood pressure control performance measures provided by HealthPartners. At 12 and 24 months, a more extensive report will be populated that will include a summary of field observations, focus group and interview data, and other data supporting recommendations for the clinics.

Field observations will be made by study staff visiting clinics in-person and speaking with clinic managers and staff as feasible and observing the rooming process. The study team will meet to discuss observations and other sources of data prior to compiling monthly reports or making recommendations. Reports will be available and shared online, and viewable across clinics.

## **10. Analysis**

## 10.A Aim 1 Primary and Secondary Analyses

The Aim 1 hypotheses pertain to the effectiveness of telehealth care, predicting that, relative to clinic-based care, it will improve SBP by a practically meaningful 5 mm Hg after 12 months of follow up (H1.1) and patient-reported outcomes (PRO) after 6 months of follow up (H1.2). H1.1 will be tested using random coefficients models in which post-enrollment SBP values will be predicted from clinic-randomized treatment group (Telehealth), time elapsed from enrollment to the SBP (YEARS), and the treatment by time interaction. The most basic form of the H1.1 model will be:

$$SBP_{ij} = \gamma_{00} + \gamma_{10} \text{Telehealth}_i + \gamma_{01} \text{YEARS}_j + \gamma_{11} \text{Telehealth}_i * \text{YEARS}_j + [u_{i0} + e_{ij}],$$

where EHR-derived SBP values documented at all qualifying encounters for 24 months will vary randomly across randomized clinics ( $u_{i0}$ ) and time ( $e_{ij}$ ). Enrolled patients will be assigned to the treatment group to which their clinic is randomly assigned, regardless of their adherence to any component of the clinic-based care or telehealth care approaches. YEARS will be scaled so that 0 represents the date of the primary care encounter at which the patient was enrolled in the study and 1 represents 365 days later. Parameter  $\gamma_{01}$  will therefore estimate the annual rate of change in SBP among clinic-based care patients, and parameter  $\gamma_{11}$  will estimate the difference in rate of SBP change among telehealth relative to clinic-based care patients. The H1.1 model will be adapted for H1.2 by replacing the YEARS component of  $\gamma_{01}$  and  $\gamma_{11}$  with a dummy indicator (6M) for whether the PRO is an enrollment or 6-month survey response.

SBP and PRO are expected to be approximately normally distributed, although the suitability of alternate error distributions and link functions will be assessed if their distributions depart from expectations. Should we observe an imbalance between study groups in the characteristics of randomized clinics, particularly in factors that moderate the fidelity with which the care models may be implemented, we may include clinic-level variables (e.g., % patients >65) as covariates or treatment modifiers, as appropriate.

SBP values are expected to decline over time among clinic-based care patients so that  $\gamma_{01} < 0$ . H1.1 will be most strongly supported if  $\gamma_{11} \leq -5.0$  and  $P < .05$ , so that the estimated rate at which SBP values improved over 12 months was at least 5 mm Hg greater among telehealth patients relative to clinic-based patients. PROs are expected to be similar at baseline but months to have improved among telehealth patients by 6 months so that  $\gamma_{11} > 0$  and  $P < .05$ .

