## **3. Study Design**

The study compares two alternative health care service designs emerging as the dominant choices for clinicians and health systems wanting to redesign and improve hypertension care outcomes. It builds on previous hypertension quality improvement initiatives and the Hyperlink study, which used telemonitoring and telephone communication between patients and clinical pharmacists. The study design incorporates many elements of pragmatic trials: few exclusion

criteria, flexible interventions delivered in routine care, and routine follow up to determine outcomes. It is a cluster-randomized comparative effectiveness trial in 20 primary care clinics (Figure 1). [Note that 21 primary care clinics were eligible to participate (see section 4.B.) and agreed to be randomized. Four of the clinics were co-located in two buildings (two practices in each) and had shared nursing leadership. Each of the co-located clinics were randomized as one unit; therefore there are 19 units of randomization. For simplicity throughout the rest of this protocol we will continue to refer to the study as including 20 primary care clinics.] The clinic-based care approach will use recommended best practices in ~10 clinics and ~1000 patients. It relies primarily on the physician-medical assistant dyad and face-to-face visits. The telehealth care approach adapts and implements a successful research-tested model in ~10 clinics and ~1000 patients. It differs from clinic-based care through the systematic use of home BP telemonitoring and home-based telehealth care coordinated by a pharmacist. Aim 1 compares outcomes that are important to patients and other stakeholders, including BP lowering, treatment side effects, patient experience, and self-care. Aim 2 evaluates the extent and between-clinic variability of the adoption, implementation, maintenance, and reach of the interventions. Data collected for Aim 2 will also be used to monitor and improve fidelity to the interventions. Please see Appendix F for a high level overview of the study design.

To ensure that the study addresses the relevant questions and concerns of patients, caregivers, clinicians, and other healthcare stakeholders, the research team includes two patient investigators, a patient advisory board (PAB), and a stakeholder advisory board. The roles, structure and function of these individuals and groups are described more fully in section 13 (Organization) and Appendix I.

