### **7.B. Secondary Aim 1 outcomes**

Aim 1 patient-reported secondary outcome measures are treatment side effects; experiences and satisfaction with hypertension care; home BP self-monitoring; and confidence in self-care. These outcome data will be collected using patient surveys. These patient-reported secondary outcome measures were selected based on 1) patient ratings of importance, 2) evidence that previous similar telehealth interventions led to improvements, 3) importance of the measure as a potential mediator of intervention effect, and 4) the measure cannot be obtained from the EHR, claims or any other routinely collected patient data. All enrolled patients will be mailed a baseline survey that includes primary patient-reported outcome measures within one week of their qualifying encounter, with telephone follow-up of non-responders. They will also be asked to complete follow-up surveys 6, 12 and 24 months later that will be administered by mail, telephone or electronically according to the patient’s preference. The secondary Aim 1 analyses will focus on patient reports in the baseline and 6 month surveys. A draft of the patient survey is included in Appendix H.

Patients’ reports of BP treatment-related side effects will be assessed using the Treatment Satisfaction Questionnaire for Medication (TSQM) and a side effect symptom checklist modeled after the PERSYVE questionnaire. The TSQM global satisfaction and effectiveness, side effects, and convenience subscales demonstrate adequate internal consistency

(Cronbach  $\alpha$  = .86-.90) and positive correlation with self-reported health. Among patients with hypertension, all three subscales were correlated with global medication satisfaction.

Patient Assessment of Chronic Illness Care (PACIC). The PACIC will quantify patient experience of hypertension care, including self-management support, along dimensions in the Chronic Care Model. The overall PACIC scale has demonstrated excellent internal consistency (Cronbach  $\alpha$  = .93; subscale  $\alpha$  = .77-.90) and adequate test-retest reliability over 3 months (overall .58; subscales .47-.68). It has been shown to be highly responsive to a telehealth intervention for hypertension.

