### 10.A.1. Aim 1 Other Analyses

We plan to explore whether treatment effects differ among patient groups defined by age, race/ethnicity, socioeconomic status, and comorbidity. While we anticipate that on average across all patient groups telehealth care will reduce SBP by 5 mm Hg more than clinic-based care, we will separately quantify the treatment effect for all H1 outcomes among targeted patient subgroups. The H1 analytic models can be easily adapted to include parameters for patient covariates as well as interactions of patient covariates with time or time by treatment.

[figure not shown]
The H1 analytic models can be readily adapted for secondary and sensitivity analyses. As presented, H1.1 assumes a linear rate of change in SBP over time. The model can be readily adapted to assess the immediate effectiveness of telehealth during the first 6 months following eligibility separately from the 6- to 12- and 12- to 24-month periods, when short-term improvements in SBP or PROs may be differentially maintained over a longer time frame. Similarly, parameters  $\gamma_{01}$  and  $\gamma_{11}$  can be allowed to vary randomly so that the rate of SBP change is different for each of the 20 randomized clinics. We could then assess, for example, whether clinic-specific rates of change are related to clinic characteristics or the fidelity with which the care model was implemented.

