### 10.A.3. Power for Aim 1 Analyses

A power analysis estimated the minimum detectable standardized effect (MDSE) for  $\gamma_{11}$  in the H1.1 model under a range of assumptions about the number of SBP values from each eligible patient and the intraclass correlation (ICC) in SBP values due to patients’ receiving care at the same clinics. We used data from patients (age 18-85, diagnosed with hypertension, current visit BP  $\geq 150/95$ , most recent previous encounter BP  $\geq 150/95$ ,  $\geq 1$  follow-up visit) seen 5/1/2017 through 2/28/2018 in the randomized Hyperlink clinics to inform power analysis assumptions. These patients (N=4967) had M=3.3 SBP over 10 months (Median=3, range 1-23), index  $M_{SBP}=159.9$ , index  $SD_{SBP}=16.1$ , all BP  $M_{SBP}=150.7$ , all BP  $SD_{SBP}=20.4$ , and a 3-level variance components model of SBP estimated  $ICC_{clin}=.003$  and  $ICC_{pt}=.28$ . For power estimates, conservatively assumed n=100 eligible patients in each of 20 clinics, 3 SBP per patient over 24 months and  $ICC_{clin}=.01-.03$  in a 2-level variance components model.

Under these assumptions, the H1.1 analysis is powered (80%,  $\alpha_2=.05$ ) to detect  $\gamma_{11} < -.124$  (when  $ICC_{clin} = .01$ ) and  $\gamma_{11} < -.174$  (when  $ICC_{clin}=.03$ ) so that an annual reduction in SBP that is  $20.4 * (.124-.174)=2.53-3.55$  mm Hg greater among patients in telehealth relative to clinic-based care clinics will be statistically detectable. Based on our previous research and systematic reviews, we believe a 5 mm Hg greater reduction in SBP will be achieved in eligible patients in telehealth care compared with clinic-based care. We assert that 5 mm Hg is a clinically important reduction in BP that substantially lowers the risk of stroke and heart disease, and even smaller reductions of 2 or 3 mm Hg have clinically important effects. The analysis should be sufficiently powered to observe clinically meaningful between-group differences in SBP reduction.

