#### 10.A.4 Missing data

Rich pre-enrollment EHR data will enable a detailed assessment of the demographic and clinical characteristics of patients who engage in each component of the clinic-based and telehealth care approaches. While the specific reasons for engagement, or lack of engagement, are not captured, it will be possible to quantify the likelihood of engagement for well-defined segments of the eligible population. Among enrolled patients, the absence of documentation of a care process or vital sign in the EHR should not be interpreted as a missing value, but rather as indicative of a care process or test not having been performed within the health system. Truly missing observations (e.g., SBP measured, value not available) will be extremely rare, undetectable, and assumed to be missing at random (MAR). EHR derived data fields will be treated as complete for these reasons.

The HealthPartners Survey Research Center will employ state-of-the-art methods to minimize unit and item nonresponse for patient-reported outcomes. The disposition of each contact attempt to complete a survey will be documented by the Survey Research Center. For mailings and email, this includes undeliverable addresses and active refusals or volunteered ineligibility due to language that are returned via these modes. For telephone surveys, these dispositions include noncontact, refusal, ineligibility, and bad telephone number. For item nonresponse, we expect less than 5% missing data on any single item. We will use a fully conditional specification approach to build a multiply imputed H1.2 dataset that assumes unobserved values resulting from item-non-response are MAR. The imputation model will include all predictors from the H1.2 analytic model as well as EHR-derived auxiliary predictors that may be correlated with PROs to improve imputation precision.

The H1.1 and H1.2 analytic models rely on maximum likelihood approaches to estimate all parameters. These models are sufficiently flexible to accommodate unbalanced data (e.g., outcomes per patient, patients per clinic) and rely on covariance structures for model estimation so that all available data from the intent-to-treat sample contribute to parameter estimation. Mixed models are predicated on a MAR assumption which is all but certain to be met in the case of H1.1, and possibly met in the imputed H1.2 dataset.

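### The primary SBP model as written has no clinic-level slope variation, although the power calculation charges a clinic design effect to the same slope; the test of the treatment-by-time effect is too liberal if clinic trends differ

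*Combined protocol and SAP*

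**What the plan says.** Section 10.A names the family as random coefficients models and introduces the equation with "The most basic form of the H1.1 model will be". The random part is a clinic term u_i0 and a residual e_ij: "where EHR-derived SBP values documented at all qualifying encounters for 24 months will vary randomly across randomized clinics". There is no patient index and no random coefficient on time. H1.2 reuses the model, with a 6-month indicator in place of time.

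Random time effects appear only in section 10.A.1 (Aim 1 Other Analyses), where the time parameters "can be allowed to vary randomly so that the rate of SBP change is different for each of the 20 randomized clinics". The stated use is to relate clinic trends to clinic characteristics or implementation fidelity.

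Section 10.A.3 reports that "a 3-level variance components model of SBP estimated" a clinic ICC of .003 and a patient ICC of .28, then powers the trial on a two-level model with clinic ICC .01-.03.

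On estimation, section 10.A.4 states: "The H1.1 and H1.2 analytic models rely on maximum likelihood approaches to estimate all parameters". It does not say ML or REML and names no degrees-of-freedom method. Section 3 explains that co-located practices were randomized together, "therefore there are 19 units of randomization", and that the text keeps saying 20 clinics for simplicity.

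**The concern.** In a cluster-randomized trial, the treatment contrast must be judged against variation between the randomized units. Here the contrast is a slope difference, so the relevant variation is how far clinics differ in their SBP trend. The written model sets that variation to zero. If clinics do differ in trend, the standard error of gamma11 is too small and the P value that decides H1.1 is too small with it. The plan gives reason to expect differences: section 1.B.1 reports substantial between-clinic variation in BP control, and Aim 2 studies between-clinic variability in implementation.

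The patient effect is a separate omission. With a patient ICC of .28 and 1 to 23 readings per patient, readings from one person are treated as independent. In H1.2, each respondent's enrollment and 6-month surveys are treated as unrelated.

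**Working it through.** **1. Reproduce the plan's detectable effect.** Inputs from section 10.A.3: 10 clinics per arm, 100 patients per clinic, 3 SBP values over 24 months, SD 20.4, two-sided 5%, 80% power. The visit spacing is not given; 0, 1 and 2 years is assumed, so the sum of squared time deviations per patient is Sxx = 2.

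MDSE = (1.960 + 0.842) × √{2(1 − ICC)(1 + 99·ICC) / (10·100·2)}

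| ICC | Design effect 1 + 99·ICC | MDSE | Plan | MDSE without design effect |
|---|---|---|---|---|
| .01 | 1.99 | .1244 | .124 | .088 |
| .03 | 3.97 | .1739 | .174 | .087 |

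The plan's figures come back only with the design effect. Under the model as written, the last column would apply at either ICC.

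**2. Clinic slope SD that the power formula implies.** The design effect adds variance (1 − ICC)·99·ICC/200 to each clinic's standardized slope, so

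SD = 20.4 × √{(1 − ICC)·99·ICC/200}

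This gives 0.79 mm Hg/yr at ICC .003 (the observed value), 1.43 at .01 and 2.45 at .03. These are inferred values; the documents give no slope SD.

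**3. Type I error of the written test, irregular visits.** Readings come from routine encounters. For three readings at random times over H years, Sxx is about 3·H²/12: 1.00 for 24 months, 0.25 for 12 months. The model's standard error is about 20.4·√{2/(1000·Sxx)} = 0.91 and 1.82 mm Hg/yr. With slope SD τ and 9 versus 10 units,

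R = √{1 + τ²(1/9 + 1/10)/SE²}, type I error = 2{1 − Φ(1.96/R)}

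| τ (mm Hg/yr) | 24 months: R, error | 12 months: R, error |
|---|---|---|
| 0 | 1.00, 5.0% | 1.00, 5.0% |
| 0.79 | 1.08, 6.9% | 1.02, 5.5% |
| 1.43 | 1.23, 11.2% | 1.06, 6.5% |
| 2.45 | 1.59, 21.7% | 1.17, 9.5% |

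Simulations of the written model (19 units, about 2000 patients, patient ICC .28, 1,500 runs, irregular or uneven visits) agree: over 24 months about 5-6%, 6-8%, 10-12% and 21-24% down the rows; over 12 months about 5-10% in all. A t test on unit-level slopes in the same simulations gave about 5-6%.

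**4. Role of the patient effect in H1.1.** With no clinic slope variation, the simulated error was 5-6% for irregular visits and about 1% for a balanced 0/1/2-year schedule (2.1% in closed form). Omitting the patient effect therefore does not inflate this test.

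**5. H1.2.** Assume that the 6-month correlation is near the 3-month PACIC test-retest value of .58 (section 7.B), and ignore any clinic-by-time effect.
- With 450 per arm at both surveys, the written SE of change is too large by 1/√(1 − .58) = 1.54.
- With the response rates of section 10.A.3 (60%, then 75%) and all data used, there are 600 and 450 per arm: √{(1/600 + 1/450)/(1/600 + 1/450 − 2·.58/600)} = 1.41.
- At d = .24, power is 82% with 450 at both surveys and 86% with 600 and 450. Paired analysis of 450 gives 98%.

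**6. After adding unit slopes.** Seventeen df remain. A z-test would then have P(|t17| > 1.96) = 6.7% with REML, or P(|t17| > 1.96·√(17/19)) = 8.1% with ML. With t on 17 df, 19 units and the step 1 schedule, the detectable difference is 2.73 mm Hg (ICC .01) to 3.84 mm Hg (ICC .03), against the stated 2.53-3.55. Power for 5 mm Hg is 99.9% and 95%.

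**The case against.** The strongest reply is that the plan is underspecified, not settled on a wrong model. It says random coefficients, calls its equation the most basic form, lists clinic slopes as available, and says in section 15 (item 4.1) that design effects from clustering and repeated measures can be checked as data accrue. That is fair, but no text commits the primary test to a clinic slope, and choosing the random structure after seeing data is what prespecification should prevent.

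The second reply is about size, and most of it stands. A reader who applies the design effects directly on the balanced schedule gets 2{1 − Φ(1.96/√DE)} = 16.5% and 32.5%, and might infer that a third of null trials would be declared positive. The documents do not support that. The ICC range is described as conservative, the observed clinic ICC is .003, visits are not balanced, and item 4.1 assesses effectiveness over the first 12 months. Against this, .003 describes variation in SBP level, not slope, and section 10.A itself uses 24 months of values.

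A reader might also infer that the missing patient effect, or maximum likelihood with 19 units, causes the inflation. Neither does in the model as written. The first leaves the SBP test near nominal or conservative. The second matters only once unit slopes are modelled, because until then gamma11 is a within-clinic contrast with very many df.

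**Conclusion.** The concern holds. The primary model as written omits the variance component against which a clinic-randomized slope should be tested, and it contradicts the power section, which includes a clinic penalty on that slope. The contradiction is shown by the reproduced .124 and .174, given the assumed 0/1/2-year spacing.

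The size is conditional on an unstated clinic slope SD. At the planning ICCs the 24-month error is about two to nearly five times nominal; at the observed ICC, or over 12 months, the excess is small to moderate. With no slope variation there is essentially none.

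The missing patient effect is a separate misspecification. Its cost falls on H1.2, where the SE of change is roughly 1.4 to 1.5 times too large if the correlation is near .58.

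**What to change.** Prespecify the primary H1.1 model with:
- a random intercept and random time slope for each of the 19 randomization units, with co-located practices as one unit;
- a patient random intercept;
- REML with a small-sample df correction such as Kenward-Roger (about 17 df).

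A patient random slope is optional, given a median of 3 readings. For H1.2, use a patient random intercept and a unit-by-time effect. Restate the power section for 19 units and t-based inference so that it matches the analysis.

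The cost is SAP wording, model code and slightly wider SBP intervals, with the detectable difference and power given in step 6 of the working.

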Patient-reported outcomes from the eligibility and 6 month surveys, corresponding to the beginning and end of intensive intervention, will be analyzed using the H1.2 model. We conservatively estimate 60% and 75% eligibility and 6 months response rates. Relative to the biologically based SBP, we anticipate higher clinic-based variance components for PROs (eg,  $ICC_{clin}=0.02-.03$ ) for PROs. The MDSE comparing 6-month PROs among telehealth relative to clinic-based care patients are  $\gamma_{11}=.239-.270$ . We expect to be able to detect 6-month differences of about 4.5 to 6 points (scale range = 0-100) on the TQSM (subscale SDs=18.7-22.6) and about 0.25 points (scale range = 1-5; SD=1.0) on the PACIC. For self-reported outcomes, a between-groups difference of Cohen’s d = .20-.30 is small, consistent with the goal of detecting meaningful differences in patient-reported side effects, care experiences, and self-management.

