self-reports of these outcomes from patient surveys. Similar to the clinical effectiveness analyses, patient reported outcomes (PROs) will be collected at enrollment and then 6, 12 and 24 months later but the contrast of interest is the enrollment to 6 month change among telehealth care relative to clinic-based care patients. Missing values resulting from non-consent, non-response, loss to follow-up and item non-response increase the likelihood of misestimating PRO models. The patient survey sampling frame will include a wealth of demographic and clinical information so that we can identify characteristics that are associated with each source of missingness and develop a plan for handling missing data (e.g., multiple imputation).

4.3 Equity of patient benefit. The clinic-based care and telehealth care intervention have both been shown effective in improving hypertension outcomes. The purpose of this work is to estimate their relative effectiveness in improving clinical and patient reported outcomes. It is not expected that either of these approaches will be sufficiently superior to the other to warrant developing stopping rules for clinical benefit. Similarly, the anticipated effect sizes are sufficiently modest and accrue over a time frame such that stopping the trial early for futility would more likely result in a Type II error than offer patients a more beneficial alternative treatment.

4.4 Safety outcomes monitoring. Both interventions have been implemented in primary care settings or systematically studied with no evidence of increased likelihood of risk to patients. It is possible nonetheless that incident diagnoses related to hypertension and antihypertensive medications (e.g., hypotension / fainting, electrolyte disturbances, renal failure) and changes in lab measures indicative of antihypertensive medication (e.g., Na, K, eGFR) may be more evident among patients in one of these two treatment groups, or among patients who are exposed to the intervention as intended. The electronic health record will document each of these safety outcomes as they occur over the course of the study. Because these are more likely to be documented in outpatient than inpatient settings the lag between occurrence and documentation will be minimal.

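### The written H1.2 model has no patient-level or clinic-by-time term, so the standard error of the patient-reported change is wrong, and the stated detectable effect belongs to a different comparison

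*Combined protocol and SAP*

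**What the plan says.** Section 10.A introduces its equation with "The most basic form of the H1.1 model will be". SBP values "will vary randomly across randomized clinics" and over time, and the bracketed error part holds only a clinic intercept and a residual. For the patient-reported outcomes, "The H1.1 model will be adapted for H1.2 by replacing the YEARS component of" γ01 and γ11 with an indicator for the 6-month survey. No random term is added.

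Section 15, item 4.2, names the target: "the contrast of interest is the enrollment to 6 month change among telehealth care relative to clinic-based care patients". Section 8.B says "All study-enrolled patients (n=2000) will be invited to complete a series of surveys", and that those who do not answer the enrollment survey are sent no more. Every 6-month response therefore has a baseline response from the same person.

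Section 10.A.3 assumes response rates of 60% and 75% and a clinic ICC of .02-.03 for these outcomes. It then states: "The MDSE comparing 6-month PROs among telehealth relative to clinic-based care patients are" .239-.270. Section 7.B gives a 3-month test-retest reliability for the PACIC of .58 overall and .47-.68 for its subscales. No enrollment-to-6-month correlation is given for any instrument.

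**The concern.** The contrast is a change within patients, but the model does not know which two surveys come from the same patient. With positive correlation between them, part of the residual cancels in the change, and the written model gives no credit for that. The reported standard error is then too large and the test conservative, so real differences of the size that section 10.A.3 calls meaningful (d=.20-.30) could be reported as null.

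The equation also lacks a term for clinics changing differently between the two surveys. That omission works in the opposite direction. The net error depends on two quantities that the plan does not state. The power paragraph does not help, because its figure does not describe γ11.

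**Working it through.** **Inputs**
- Patients: "conservatively assumed n=100 eligible patients in each of 20 clinics" (section 10.A.3), so 1,000 patients and 10 clinics per arm.
- Enrollment surveys: 60% gives 600 per arm, or 60 per clinic. Six-month surveys: 75% of those gives 450 per arm, or 45 per clinic.
- Clinic ICC .02-.03 (section 10.A.3). Total variance is set to 1.
- Two-sided α .05 and 80% power are stated for H1.1 and assumed for H1.2; the multiplier is 1.960 + 0.842 = 2.802.
- Within-patient correlation ρ = .47, .58, .68: an assumption, borrowed from the 3-month PACIC values.
- Correlation c of a clinic's effect between the two surveys: an assumption; the documents give none.
- All results use the normal approximation.

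**1. The plan's own figure.** For one time point with m responders per clinic, MDSE = 2.802 × √(2[1+(m−1)ICC]/(10m)).
- m=60, ICC .02: 1+59×.02 = 2.18; √(2×2.18/600) = .0852; MDSE .239.
- m=60, ICC .03: 1+59×.03 = 2.77; √(2×2.77/600) = .0961; MDSE .269 (plan: .270).
- m=45: .256 and .284.

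The stated range is thus a single-time comparison of 600 with 600 patients. It does not apply the 75% 6-month response and is not the change contrast. On that basis, power at d=.20 is 65% (ICC .02) or 55% (ICC .03).

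**2. Standard error of γ11 reported by the written model.** √(2(1−ICC)(1/600+1/450)). At ICC .02: √(1.96×.003889) = .0873. At ICC .03: √(1.94×.003889) = .0869.

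**3. True standard error of the same estimator, stable clinic effects (c=1).** √(2(1−ICC)(1/600+1/450−2r/600)), with r = (ρ−ICC)/(1−ICC). At ρ=.58 and ICC .02: r = .571; √(1.96×.001984) = .0624. The ratio is .0873/.0624 = 1.40.

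**4. Power at d=.20.**
- As written: Φ((.20−1.96×SE written)/SE true). At ρ=.58 and ICC .02: Φ(.0289/.0624) = 68%.
- With a patient term: SE = √(2(1−ICC)[(1−r²)/450 + r²/600 + 1/600 − 2r/600]) = .0594; Φ(.20/.0594−1.96) = 92%.

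| ρ | SE written / true | Power as written | Power with patient term |
|---|---|---|---|
| .47 | 1.28 | 67% | 85-86% |
| .58 | 1.40 | 68% | 92% |
| .68 | 1.53-1.54 | 70% | 97% |

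A simulation at ρ=.58 with 20 clinics and 2,500 runs gave 67.6% and 91.8%.

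**5. Clinic effects that move between surveys.** Add 4×ICC×(1−c)/10 to each true variance, and use r = (ρ−c×ICC)/(1−ICC). At c=.8 the addition is .0016 (ICC .02) or .0024 (ICC .03). With ρ=.58:
- True SE is .0739 or .0790, so the written SE is 18% or 10% too wide.
- Power is 65% as written, against 80% or 74% with both terms modelled.
- At ICC .03 the ratio falls to 1.01 at c=.7 and .94 at c=.6, so the written SE becomes too small. At ICC .02 the crossover is near c=.5.

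**6. A patient term without a clinic-by-time term.** Actual size = 2Φ(−1.96 × SE without clinic-by-time variance / SE with it). At ρ=.58 this is 7.7% (ICC .02) or 9.1% (ICC .03) at c=.9, and 10.4% or 13.2% at c=.8.

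**The case against.** The strongest reply is that the plan never decides against linking. It presents the equation as a basic form within the random-coefficients family, section 10.A.4 refers to covariance structures without naming one, section 10.A.3 fits a three-level model to SBP, and section 15 intends to check repeated measures within patients, though for clinical outcomes. That stands: the fault is under-specification. But none of these passages commits H1.2 to a patient term, and an analyst who follows the equation gets a wrong standard error.

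The second reply concerns size. A reader might infer that every H1.2 interval is 40% too wide and that power drops from 92% to 68%. The documents do not support that as a fact. The .58 is a 3-month value for one instrument; the TSQM, the symptom checklist, CG-CAHPS and the self-care items have no such value. The 92% is what a linked model would reach if clinic effects were stable, not something the plan promised: its own MDSE implies 55-65% at d=.20, slightly below what the written model delivers.

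The third reply is that stable clinic effects are the most favourable case. Section 3 expects implementation to vary between clinics, and section 10.A.1 allows clinic-specific rates of SBP change. This also stands, and it changes the remedy, because a patient intercept alone could replace a conservative test with an anti-conservative one.

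**Conclusion.** The point holds in conditional form. The written H1.2 model gives a wrong standard error for γ11. With stable clinic effects and ρ of .47-.68, it is 28-54% too wide and power at d=.20 is about 67-70% instead of 85-97%. At c=.8 and ρ=.58 the excess is 10-18%, and power is 65% against 74-80%. With more clinic-by-time variance the sign can reverse, so the documents do not establish that the test is conservative in all cases. These ranges rest on a borrowed correlation, an assumed c and a normal approximation.

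The mismatch in section 10.A.3 needs no assumed correlation: .239-.270 is neither the γ11 contrast nor adjusted for 6-month response. H1.2 is secondary, but section 10.A judges it by P<.05, so its error structure should be fixed before the data are seen.

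**What to change.** In section 10.A, write the H1.2 model out in full: a patient random intercept nested in clinic (or an unstructured 2×2 within-patient covariance) together with the clinic intercept and a clinic-by-time random term. Keep all enrollment-survey responders, including those without a 6-month survey.

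In section 10.A.3, restate the detectable effect for γ11 under that model with 600 and 450 surveys per arm, over a stated range of within-patient correlation and of clinic correlation between surveys.

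The cost is SAP wording, a recalculated figure and two more variance parameters. One of these is estimated from only about 20 clinics and will be imprecise. No new data or patients are needed.
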